6.3 Eligibility Criteria (infant)

- Evidence of a signed and dated informed consent form signed by the parent(s)
- Parent(s) willing and able to comply with scheduled visits and other study procedures

6.4 Other considerations (maternal vaccination)

- Clinically significant pregnancy-related conditions according to medical judgement
- Clinically significant acute illness at the time of vaccination (cardiovascular, endocrine, gastrointestinal, hepatic, renal, neurological, respiratory, or other medical disorders) that is actively causing symptoms that could, in the opinion of the investigator, impact the assessment of reactogenicity or other study assessments. Participants may have planned study vaccination deferred for a later date, but these criteria are not exclusionary for study enrolment. Participant may be vaccinated once symptoms have resolved or are stabilised for > 3 days. Out-of-window study vaccination is allowed for this reason.
- Fever (body temperature $\geq 38.0^{\circ}\text{C}$ [100.4°F]) within 24 hours prior to the planned vaccination. Participants may be vaccinated once the fever has resolved and there has not been any temperature measured as being $> 38^{\circ}\text{C}$ for > 3 days. Out-of-window study vaccination is allowed for this reason.

7 TRIAL PROCEDURES

Screening + study visit 1 (Maternal)

This visit will take place between 13 0/7 – 27 6/7 gestational weeks (for the earlier gestational weeks group) or between 28 0/7 – 34 0/7 gestational weeks (for the later gestational weeks group) at the participating institution. Eligibility will be confirmed, the study will be discussed in more detail and women will be asked to sign a consent form. They will then be asked about demographic details (including NHS number), past medical history, receipt of any prior dose of a COVID-19 vaccine, details of the current pregnancy including the results of antenatal screening and scans to ensure that they are eligible for the study. The participant's antenatal medical notes will be reviewed. Details will be collected about concomitant medication. A physical examination will be performed, and vital signs, height and weight will be recorded. Immunogenicity blood samples will be obtained.

Cohort 1, 2, 3: Participants will be randomised to a single group to receive one type of COVID-19 vaccine with the first dose to be given at visit 1.

Cohort 4: Participants will receive the same vaccine as given pre-pregnancy or during their first trimester (0 0/7 – 12 6/7 gestational weeks) and randomised to either receiving the booster dose before or after 26 weeks' gestation.

Vaccination will be given by members of the study team who are trained and experienced in vaccine administration and in emergency procedures in the event of an allergic reaction. They will have access to emergency medication and equipment. The vaccinations will be given according to the advice in the “Green Book” and the Summary of Product Characteristics (SmPC). An eDiary will be set up for the participant and they will be given instructions to complete the diary regularly for 28 days following vaccination. The participant will be observed for a period of 20 minutes following vaccination to assess for allergic adverse events.

Study visit 2 (Maternal) all cohorts

14 days (10 days – 21 days) after first vaccination review by telephone call.

- SAE / AESI / MAAE check
- Concomitant medication check
- eDiary review

Study visit 3 (Maternal) all cohorts

Day 28-42 following the first vaccination at the participating institution.

- SAE / AESI / MAAE check
- Concomitant medication check
- eDiary review
- Targeted physical examination if indicated
- Immunogenicity blood samples will be collected
- **Cohort 1.**
 - Vital signs pre-vaccination
 - **Vaccination with COVID-19 vaccine if randomised to the short interval boost or dTaP/IPV if randomised to the long boost arm and has not previously received pertussis vaccine.**
 - Observation period post-vaccination for 20 minutes
- **Cohort 2.**
 - Vital signs pre-vaccination

- **Vaccination with COVID-19 vaccine if randomised to the short interval boost or no vaccine or dTaP/IPV if randomised to the long interval boost arm and has not previously received pertussis vaccine. If dTaP/IPV vaccination is requested, it should be given by 32 weeks' gestation and with an interval of at least 1 week before / after receipt of COVID-19 vaccine.**
- Observation period post-vaccination for 20 minutes
- **No vaccination for cohort 3 (28 0/7 – 34 0/7 gestational weeks at recruitment) and cohort 4 (COVID-19 vaccine received pre-pregnancy / first trimester (0 0/7 – 12 6/7 gestational weeks)).**

Study visit 4 (Maternal) Cohort 1 and 2 only

Day 56-84 following the first vaccination (or 28-42 days post-short interval boost dose) at the participating institution.

- SAE / AESI / MAAE check
- Concomitant medication check
- Diary card review if applicable
- Targeted physical examination if indicated
- Immunogenicity blood samples will be collected

- **Cohort 1.**
 - Vital signs pre-vaccination
 - **Vaccination with COVID-19 vaccine if randomised to the long interval boost or dTaP if randomised to the short interval boost arm and has not previously received the pertussis vaccine**
 - Observation period post-vaccination for 20 minutes
 - eDiary review

- **Cohort 2.**
 - Vital signs pre-vaccination
 - **Vaccination with COVID-19 vaccine if randomised to the long interval boost or no vaccine or dTaP/IPV if randomised to the short interval boost arm and has not previously received pertussis vaccine. If dTaP/IPV vaccination is requested, it should be given by 32 weeks' gestation and with an interval of at least 1 week before / after receipt of COVID-19 vaccine.**
 - Observation period post-vaccination for 20 minutes
 - eDiary review

- **No visit 4 for cohort 3 (28 0/7 – 34 0/7 gestational weeks at recruitment) and cohort 4 (COVID-19 vaccine received pre-pregnancy / first trimester (0 0/7 – 12 6/7 gestational weeks)).**

Study visit 5 (Maternal) Cohort 1 and 2 only

Day 84-112 following the first vaccination (or 28-42 days post-long boost dose) at the participating institution / participant home.

- SAE / AESI / MAAE check
- Concomitant medication check
- eDiary review if applicable
- Targeted physical examination if indicated
- Immunogenicity blood samples will be collected
- **No visit 5 for cohort 3 (28 0/7 - 34 0/7 gestational weeks at recruitment) and cohort 4 (COVID-19 vaccine received pre-pregnancy / first trimester (0 0/7 – 12 6/7 gestational weeks)).**

Study visit 6 (Maternal) Cohort 1, 2 and 4 only

Day 112-140 following the first vaccination (or 56-84 days post second COVID-19 vaccine dose at the participating institution / participant home. This visit need only take place if the visit window starts before the due date.

- SAE / AESI / MAAE check
- Concomitant medication check
- eDiary review if applicable
- Targeted physical examination if indicated
- Immunogenicity blood samples will be collected
- **No visit 6 for cohort 3 (28 0/7 – 34 0/7 gestational weeks at recruitment).**

Study visit 7 (Delivery, maternal / infant)

Delivery at the participating institution.

- Targeted physical examination if indicated
- Immunogenicity maternal blood samples will be collected. These samples can be obtained by a member of the study team or a clinical member of staff. If blood sampling is not performed at delivery, women will be asked if a blood sample can be obtained from them within the first week following delivery and if a cord sample is not obtained parents will be asked if we can take a blood sample from the infant within the first week following delivery.
- Cord blood sample taken (at selected sites)

- Infant examination by clinical team

Study visit 8 (postnatal) only for participants in cohort 3 and / or in the breast milk sub-study

0 – 7 days post delivery where possible at the participating institution for those in the breast milk sub-study group and those due vaccination in cohort 3.

- SAE / AESI / MAAE check
- Concomitant medication check
- Targeted maternal physical examination for participants in cohort 3 only
- Colostrum sample collection (at selected sites). Participants who have agreed to take part in the breast milk sub-study will be asked if they still plan to breastfeed and if they are happy to provide a sample of colostrum. If women are still willing to take part in the study, they will be provided with information about colostrum sampling and containers and instructions for the collection of the sample.
- Participants who are taking part in the breast milk sub-study will hand express a sample of colostrum from each breast. Participants will be provided with containers and instructions for the collection of subsequent samples
- Vital signs pre-vaccination
- **Vaccination with COVID-19 vaccine for those in cohort 3 (28 0/7 – 34 0/7 gestational weeks at recruitment)**
- Observation period post-vaccination for 20 minutes
- eDiary set up for those receiving a vaccine

Study visit 9 (postnatal)

12 - 16 days post delivery where possible at the participating institution for those in the breast milk sub-study group. All other participants can be reviewed at this visit by a telephone call.

- SAE / AESI / MAAE check
- Concomitant medication check
- Breast milk sample collection (at selected sites). Women will be asked to provide a sample of breast milk from each breast. This sample can be collected by the woman in advance and collected by a member of the research team if this is a remote visit.
- There will be further randomisation to determine whether the infant bloods are taken at 4-6 weeks after birth or at 10-12 weeks after birth except cohort 3 (cohort 3 will have infant and maternal blood samples taken at **28-42 days** post-delivery).
- eDiary check for those who received a vaccine post-delivery (cohort 3)

Study visit 10 (postnatal)

28-42 days OR 70-84 days post delivery at the participating institution / participant home (cohort 3 will have infant and maternal blood samples taken at 28-42 days post-delivery).

- SAE / AESI / MAAE check
- Concomitant medication check
- Targeted maternal physical examination if indicated
- Maternal immunogenicity blood sample collection
- Infant blood sample collection This will be a venous sample where possible, taken by an experienced member of the research team.
- eDiary check for those who received a vaccine post-delivery (cohort 3)

Study visit 11 (postnatal)

182 days (-/+ 14 days) post delivery review by telephone call.

- SAE / AESI / MAAE check
- Concomitant medication check

Study visit 12 (postnatal)

364 days (-/+ 14 days) post delivery at the participating institution / participant home.

- SAE / AESI / MAAE check
- Concomitant medication check
- Immunogenicity blood sample collection
- Infant examination and neurodevelopmental assessment – “Ages and Stages” Questionnaire if not already completed by a healthcare professional during routine care.

Contraindications to vaccination

Clinically significant pregnancy-related conditions according to medical judgement

Clinically significant acute illness at the time of vaccination

Fever (body temperature $\geq 38.0^{\circ}\text{C}$ [100.4°F]) within 24 hours prior to the planned vaccination

Symptomatic participants

Participants will be counselled at enrolment that should they receive a positive SARS-CoV-2 test (e.g. an antigen detection or nucleic acid amplification test, for example, via test and trace or occupational health services) they should contact the trial team on receipt of the positive result.

Once the participant has conveyed their result to the study team, and the study team confirm an appropriate test has been used (via verbal discussion with participant as to how testing was obtained). Confirmatory documentation may be sought from the participant (such as a forwarded email or a picture of a lateral flow assay result, but this is not essential). Cases of positive COVID-19 maternal infection will be noted.

Symptomatic infants will also receive an appropriate SARS-CoV-2 test and if positive an appointment will be arranged to review the participant at the relevant study site. At this visit blood samples for safety (FBC, Biochemistry, CRP and others if deemed clinically relevant) and immunology (PBMCs and serum for cellular and humoral immune responses) will be obtained. Vital signs and other clinical data will be recorded.

Participants (mothers/infants) will also be provided with a symptom diary to complete both solicited and unsolicited symptoms for at least 7 days and until symptom resolution (excepting persistent cough and anosmia/dysgeusia as these are recognised to be able to continue for extended periods). Additional visits on this pathway may be arranged at the clinical discretion of the investigator.

Lost to follow up

If contact with a participant is lost during the study, we will attempt to contact them by phone or email on three separate occasions. If we are unable to make contact using the information we have we will contact their GP to check if contact details have changed. We will specifically ask for consent from the pregnant woman to do this. We will ask for additional consent to use NHS number to trace the GP if the GP has changed since the start of the study. If there are new contact details, we will try again to make contact by phone or email on three separate occasions. If contact is still not possible or if the details we had been using previously were correct we will send a letter to the participant asking them to make contact with the research team. Participants will be considered lost to follow up if they have not made contact with the study team by two weeks following their estimated date of delivery.

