- SARS-COV-2 IgG-specific antibody concentration, (and neutralizing antibody titres in a subset) against SARS-COV-2 measured on the cord blood sample collected at delivery, or on a blood sample collected from the infant within 3 days after birth (if no cord blood sample can be obtained)
- The ratio between cord blood and maternal SARS-COV-2 IgG-specific antibody concentrations or an infant blood sample collected within 72 hours after birth (if no cord blood sample can be obtained)
- SARS-COV-2 IgG-specific antibody concentrations and Neutralizing antibody titres against SARS-COV-2 in infants born to vaccinated mothers at Day 28 to 42 or Day 70 to 84 post-delivery.

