
 To evaluate the transfer of SARS-CoV-2 specific antibodies from mothers vaccinated with COVID-19 vaccines, according to different regimens, to their infants at the time of delivery 	
 SARS-COV-2 IgG-specific antibody concentration, (and neutralizing antibody titres in a subset) against SARS-COV-2 measured on the cord blood sample collected at delivery, or on a blood sample collected from the infant within 3 days after birth (if no cord blood sample can be obtained) 	
Cord blood sample taken at delivery or infant blood sample taken within 3 days of life (if no cord blood sample can be obtained).

	
 The ratio between cord blood and maternal SARS-COV-2 IgG-specific antibody concentrations or an infant blood sample collected within 72 hours after birth (if no cord blood sample can be obtained) 	

 To evaluate the kinetics of SARS-CoV-2 specific maternal antibodies in infants born to mothers vaccinated with COVID-19 vaccine(s), up to 3 months after birth 	
 SARS-COV-2 IgG-specific antibody concentrations and Neutralizing antibody titres against SARS-COV-2 in infants born to vaccinated mothers at Day 28 to 42 or Day 70 to 84 post- delivery 	
Infant blood sampling between day 42 and day 84 post-delivery

 To assess the effect of gestational age at vaccination, interval between vaccination and delivery, maternal age, health status, vaccine type and schedule on immune responses and duration of immune responses in vaccinated women and on placental transfer and antibody kinetics in their infants 	
 SARS-COV-2 IgG-specific antibody concentration, (and neutralizing antibody titres in a subset) against SARS-COV-2 measured on the cord blood sample collected at delivery, or on a blood sample collected from the infant within 3 days after birth (if no cord blood sample can be obtained) The ratio between cord blood and maternal SARS-COV-2 IgG-specific antibody concentrations or an infant blood sample collected within 72 hours after birth (if no cord blood sample can be obtained) 	
Maternal blood sample taken at delivery and cord blood sample taken at delivery or infant blood sample taken within 3 days of life (if no cord blood sample can be obtained).

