7.7 Trial assessments

Blood samples will be obtained from women prior to vaccination, day 28-42, day 56-84, day 84-112, day 112-140 if not delivered already, at delivery, at 4-12 weeks after delivery, and at day 364 after delivery. A cord blood sample at selected sites will be obtained at delivery and if this is not collected a blood sample can be obtained from infant. All infants will have a blood sample taken at day 42 – 84 after birth. Colostrum samples will be obtained from women participating in the breastfeeding sub-study at 72 hours after delivery where possible and breast milk at day 14 after delivery where possible.

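### The infant sample that replaces missing cord blood may be drawn up to a week after birth at visit 7, but the cord IgG and transfer-ratio endpoints accept it only within 72 hours

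*Protocol*

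**What the plan says.** The procedural text and the endpoint text give different windows for the same sample.

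- **Protocol section 7, Study visit 7 (delivery):** if there is no cord sample, parents are asked whether the team can "take a blood sample from the infant within the first week following delivery". The same bullet gives the mother an equal allowance when blood is not taken at delivery: "women will be asked if a blood sample can be obtained from them within the first week following delivery". The next bullet reads "Cord blood sample taken (at selected sites").
- **Section 3.5, IgG concentration endpoint:** measured on cord blood, "or on a blood sample collected from the infant within 3 days after birth (if no cord blood sample can be obtained").
- **Section 3.5, ratio endpoint:** cord to maternal concentration, "or an infant blood sample collected within 72 hours after birth (if no cord blood sample can be obtained"). No window is given for the maternal sample in the denominator.
- **Section 3.7, timepoint column:** "infant blood sample taken within 3 days of life (if no cord blood sample can be obtained"). The Trial Summary repeats the 3-day and 72-hour limits.
- **Section 7.7:** "if this is not collected a blood sample can be obtained from infant", with no window.

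The infant kinetics endpoint in sections 3.5 and 3.7 is set at days 28 to 42 or 70 to 84 after delivery. Section 7.11.2 requires sample labels to carry the date of sampling and allows up to 5 ml of infant blood.

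**The concern.** Sites work from the visit instructions, and a site that follows visit 7 exactly can draw blood from a newborn on days 4 to 7 that the endpoint definition does not accept. That sample is too late to stand in for cord blood and too early for the kinetics endpoint, so no stated infant endpoint covers it.

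There are two possible outcomes. If the endpoint definition is applied, the value is lost after the infant has been bled. If the sample is used anyway, the result mixes placental transfer with several days of postnatal decay. The data concerned serve two secondary infant objectives: transfer of antibody at delivery, and the effect of gestational age, interval, vaccine type and schedule on that transfer.

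This is more than a matter for the analysis plan, because the protocol itself fixes both windows and no later analysis rule can recover a sample taken too late.

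**Working it through.** **Step 1. Compare the windows.**

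| Place in the protocol | Window for the substitute infant sample |
|---|---|
| Trial Summary, both endpoints | 3 days / 72 hours |
| Section 3.5, IgG endpoint | 3 days |
| Section 3.5, ratio endpoint | 72 hours |
| Section 3.7, timepoint | 3 days of life |
| Section 7, visit 7 | first week |
| Section 7.7 | none stated |
| Section 16.3 (Appendix 4) schedules | infant blood listed only at V10 |

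Three days is 3 × 24 = 72 hours, so the endpoint texts agree with each other and visit 7 is the outlier. The gap is days 4 to 7. No other section says how a sample in that gap is classified. The protocol gives no numerical figure on this point to reproduce.

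**Step 2. Decay in the infant, with the mother sampled at delivery.** Input: infant IgG half-life h, which is not in the protocol and is assumed to be 20 to 60 days. The fraction of the birth level left at day t is 2^(−t/h). The extra effect of day 7 against day 3 is 2^(−4/h).

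| h (days) | Day 3 | Day 7 | Day 7 / day 3 | Further fall |
|---|---|---|---|---|
| 20 | 0.901 | 0.785 | 0.871 | 13% |
| 30 | 0.933 | 0.851 | 0.912 | 9% |
| 40 | 0.949 | 0.886 | 0.933 | 7% |
| 60 | 0.966 | 0.922 | 0.955 | about 5% (4.5%) |

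With a maternal sample at delivery, the ratio scales by the same factors. About 3 to 10% of the fall is already possible inside the 72-hour window. The longer window adds about 5 to 13% at its far end.

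**Step 3. Only some pairs late.** If a share s of pairs is sampled at day 7 and the rest at birth level, the geometric mean ratio is multiplied by 2^(−7s/h):

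- s = 25%: 0.941 (h = 20) to 0.980 (h = 60)
- s = 50%: 0.886 to 0.960

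**Step 4. Mother also sampled at day 7.** Assume a maternal half-life m of 30 to 100 days, again not in the protocol. The ratio is multiplied by 2^(−7/h) / 2^(−7/m):

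- h = 20, m = 100: 0.824
- h = 30, m = 30: 1.000
- h = 60, m = 30: 1.084

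The direction is therefore not fixed once the maternal sample is late as well.

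**Step 5. Cord sample at birth, mother at day 7.** The factor is 1 / 2^(−7/m), which is 1.050 (m = 100) to 1.176 (m = 30). Tightening the infant window alone would leave this mismatch in the ratio.

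**The case against.** The strongest case on the other side accepts the mismatch and disputes its weight.

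- **How often the substitute is used.** Because cord blood is limited to selected sites, a reader might infer that the infant sample is the usual route elsewhere. The protocol does not show this. It gives no number or share of cord sites. Sections 7 and 7.7 word the infant sample as something parents are asked for or that can be obtained, and the Appendix 4 schedules list infant blood only at V10. The project description in Appendix 7 mentions cord sampling without a site limit. An optional fallback is the safer reading, and the contradiction stands on either one.
- **Direction.** A reader might also infer that late infant samples always lower the ratio. Step 4 shows that they need not, because the maternal sample has the same one-week allowance.
- **Size.** The 5 to 13% compares the two extremes, day 7 and day 3, under an assumed half-life. With a quarter of pairs late, the total fall from birth level is 2 to 6%. This stands.
- **Between-arm comparisons.** Randomisation is stratified by site (section 7.3.1), so site differences in sample type and timing should be roughly balanced across arms. This stands as partial protection, but it does not protect the absolute ratio.
- **Left to the analysis plan.** Handling of out-of-window samples is commonly placed there, and the sampling date on the label lets age in days be derived. That is fair for classification, but it does not resolve two conflicting collection windows in the protocol.
- **Choice of window.** Widening the endpoints to seven days would reconcile the text equally well and keep the data. It is a legitimate alternative if age at sampling is then handled in the analysis.

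**Conclusion.** The contradiction is exact and nothing in the protocol resolves it: visit 7 permits a substitute infant sample on days 4 to 7 that both cord-equivalent endpoints exclude. That conclusion rests on the text alone.

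The numerical consequence is modest and conditional. It requires late samples to be used, an assumed infant half-life of 20 to 60 days, and a maternal sample taken at delivery. With both samples at day 7, and a maternal half-life of 30 to 100 days, the factor runs from about 0.82 to 1.08. The effect falls mainly on the absolute transfer ratio. The primary immunogenicity endpoint, maternal IgG at delivery, does not use the infant sample and is unaffected by its window. The point is worth correcting because the correction is cheap and avoids drawing newborn blood that the endpoint would then reject.

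**What to change.** Reconcile the passages to one window. The simplest change is to the visit 7 infant window, bringing it to the 72 hours already stated in the Trial Summary and sections 3.5 and 3.7, and to repeat it in section 7.7. In the same edit:

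1. State the window for the maternal sample used in the ratio. This can be a rule for the ratio only.
2. Record time since birth for both the infant and the maternal sample. The label already carries the date, so the addition is the time of day.
3. Keep any later infant sample out of the main cord IgG and ratio analyses, and report it only as supplementary, with age at sampling. It should not be moved into the kinetics endpoint, whose windows of days 28 to 42 and 70 to 84 also exclude it.

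If the sponsor prefers seven days for feasibility, the endpoint definitions should be widened instead and age at sampling handled in the analysis.

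The cost of the 72-hour option is a short text edit and one or two time fields on the form. The downside is that infants reachable only on days 4 to 7 would contribute no cord-equivalent value.
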